6.3.8.2. Compliance in the extension study

Linzagolix/Placebo Grey blister (200 mg or matching placebo), Linzagolix/Placebo Pink blister (75 mg or matching placebo) and ABT/Placebo compliances from the study treatment accountability page will be summarized on the extension treatment period and overall (main and extension treatment period) by treatment group.

Compliance in extension is defined as the total used count of Grey blister/Pink blister/ABT from the Month 12 or Withdrawal Extension accountability pages divided by end of treatment date in Extension – first dose date in Extension+1.

CRS-BS-TP-000005 V 2.0

Compliance overall is defined as the sum of total used count of Grey blister/Pink blister/ABT from the Month 6 and Month 12 or Withdrawal Extension accountability pages divided by end of treatment date in Extension – Day 1 date+1.

If Linzagolix/Placebo and ABT/Placebo compliances from accountability data are missing, compliance will be computed from daily diary data:

Compliance will be computed as the number of days with pink tablet/grey tablet/red capsule taken *100 divided by the number of days in the period (end of treatment - first dose date in Extension+1 or end of treatment date – Day 1 +1 date for overall compliance). Data from "Today" will be used primarily. If data from today is missing, date from "Yesterday" will be considered. If the e-diary is not completed for a day (neither "Today" nor "Yesterday), it will be assumed that no drug was taken on that day.

Study treatment overdose and misuse will be reported in a listing.

Compliance will be reported in a listing.

6.4. Efficacy Evaluation

Efficacy analysis will be conducted using the Treatment Extension Analysis Set, the Follow-up Extension Analysis Set and the Per Protocol Extension Analysis Set when specified. Data from the main study, the extension study and the Month 6 Extension follow-up will be summarized and listed as relevant.

Efficacy endpoints will be derived in the same way as in the main study. The same criterion for defining a subject as being a responder by having a clinically meaningful reduction in DYS and in NMPP, along with a stable or decreased use of analgesics for EAP, will be used as per the criteria used in the main study.

6.4.1. Meaningful Change Threshold Estimation

6.4.2. **Primary efficacy analysis**

6.4.2.1. Primary Endpoint Specifications

The primary efficacy analysis aims to estimate the effect of linzagolix versus placebo on DYS and NMPP over the last 28 days up to and including the Month 12 visit or, for subjects who discontinued randomized treatment prior to the Month 12 visit, over the last 28 days of randomized treatment (i.e. 28-day period before last treatment administration date in Extension). Use of analgesic medication for EAP will be included in the responder definitions. A responder for each of the co-primary endpoints needs to demonstrate both a reduction in pain (DYS or NMPP, depending on the endpoint) and a stable or decreased use of analgesics for EAP. Any subject who does not meet both of these criteria will be defined as a non-responder.

CRS-BS-TP-000005 V 2.0

For each of the co-primary endpoints, the criterion for defining a subject as a responder over the last 28 days of randomized treatment up to the Month 12 visit will include a reduction of 1.10 or greater from baseline in Dysmenorrhea and reduction of 0.80 or greater from baseline in Non-Menstrual Pelvic Pain, as well as stable or decreased use of analgesics for EAP, i.e. thresholds obtained at the Month 3 meaningful change threshold analysis. The thresholds obtained at the Month 6 meaningful change threshold analysis will also be used: reduction of 1.25 or greater for Dysmenorrhea and reduction Pelvic Pain.

Mean pelvic pain scores for DYS and for NMPP will be calculated by averaging over the corresponding 28 calendar days immediately prior to and including the last treatment administration day. DYS will use days with uterine bleeding, defined as those days on which the subject records any uterine bleeding or spotting in the subject eDiary; NMPP will use days with no uterine bleeding. If a subject's mean score for DYS is undefined numerically because her daily eDiary reports indicate that she did not experience uterine bleeding on any days during the 28 calendar day period, then the mean score for DYS will be set equal to zero (which reflects the absence of any DYS during that reporting time period). Similarly, if a subject's diary reports indicate that she only experienced days with uterine bleeding during the period, then the mean score for NMPP will be set equal to zero. For subjects who discontinue treatment prior to Month 12 the last available observations prior to discontinuation will be used, in order to estimate the treatment effect while under treatment, that is the 28 calendar days immediately prior to and including the last dose date. The baseline mean overall pelvic pain scores for DYS and NMPP will be calculated by averaging over the two baseline menstrual cycles (as defined in section 6.2.2), which may not be exactly 28 days each. For both DYS and NMPP, responses of "None," "Mild," "Moderate," and "Severe" will be assigned a score of 0, 1, 2, and 3, respectively.

For the assessment of stable or decreased use of analgesics for EAP (assessed separately for DYS and NMPP), the analgesic use for any defined period will be based on the mean of the total pill count for each class of rescue analgesics (endometriosis-associated). The total pill count for each class of rescue analgesic is the sum of the pill count of the corresponding class of rescue analgesic, as reported in the eDiary during the time period of interest. Baseline analgesic use will be calculated as the mean of the daily pill count of analgesics over the two baseline menstrual cycles (as defined in section 4.5.2 of main study SAP). For the purposes of determining a stable or decreased use of analgesics, the averaging will be done over the same calendar days as used for the pelvic pain scores (i.e. for DYS days with uterine bleeding, defined as those days on which the subject records any uterine bleeding or spotting in the subject eDiary; for NMPP days with no uterine bleeding). The evaluation of stable or decreased use of analgesics will be done per the specification in 9.1 9.1 Appendix A.

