6 OBJECTIVES

6.1 EFFICACY OBJECTIVES

6.1.1 Primary

The primary objective of this extension study is to assess the maintenance of efficacy of linzagolix administered orally once daily for up to an additional 6 months (for up to 12 months of treatment in total) in women who have already completed 6 months of linzagolix treatment at a dose of 75 mg alone or 200 mg in combination with ABT (E2 1 mg / NETA 0.5 mg) in the management of moderate to severe EAP in women with surgically confirmed endometriosis. The two co-primary efficacy endpoints will be clinically meaningful reduction over the last 28 days of randomized treatment up to the Month 12 visit, along with a stable or decreased use of analgesics for EAP for 1) dysmenorrhea (DYS) and for 2) non menstrual pelvic pain (NMPP).

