7 ENDPOINTS

7.1 EFFICACY ENDPOINTS

7.1.1 Primary

The two co-primary, composite efficacy endpoints are clinically meaningful reduction from baseline to the last 28 days preceding the Month 12 visit (the 4-week period preceding Month 12 visit) along with a stable or decreased use of analgesics for EAP, in the mean daily assessment of 1) DYS and of 2) NMPP measured on a Verbal Rating Scale (VRS) using an electronic diary (eDiary).

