8 STUDY DESIGN

This is a prospective, randomized, double-blind study.

Subjects who have completed the 6-month Treatment Period in 18-OBE2109-003 - Edelweiss 3 study (herein referred to as main study) will be invited to enter the present extension study. Month 6 visit of

the main study is a decision point for Subjects to either end treatment and enter a post-treatment follow up (part of the main study), or to opt for a 6-month treatment extension.

The extension study starts at the Month 6 visit of the main study. Subjects will be required to sign a specific informed consent form (ICF) for this extension study. Only subjects who have completed the full 6-month Treatment Period in the main study and meet the inclusion criteria will be eligible for entry in the extension study.

All subjects will receive once daily either linzagolix 75 mg alone (with ABT placebo) or 200 mg combined with ABT for 6 months. Subjects who received placebo during the main study will be randomized to either linzagolix 75 mg alone (with ABT placebo) or linzagolix 200 mg with ABT. Subjects who received active treatment during the main study will continue with the same treatment.

After end of treatment in the extension study (6-month treatment period: from Month 6 to Month 12), subjects will enter a post-treatment Follow-Up Period of 6 months with no investigational medicinal product (IMP).

The total duration of the present extension study will be 12 months.

A schematic of the study design is shown in Figure 1.

[figure not shown]

Figure 1 : Study design

All subjects will receive once daily either linzagolix 75 mg alone (with ABT placebo) or linzagolix 200 mg combined with low dose ABT for 6 months. ABT is a combination of estradiol (E2) 1 mg and norethisterone acetate (NETA) 0.5 mg.

Since linzagolix 75 mg and 200 mg tablets have a different appearance, a double-dummy design will be used in order to maintain the blinding of the study.

Linzagolix/placebo tablets will be provided in monthly treatment kits, packaged, labelled and administered in the same manner to protect the blinded nature of the trial.

ABT/placebo treatments will be supplied as 3-monthly kits, packaged, labelled and administered in the same manner to protect the blinded nature of the trial.

Each treatment kit will be labelled with a unique kit number. Treatment kit numbers will be provided through IWRS.

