13.5 DATA ANALYSIS

The primary objective of this extension study is to assess the maintenance of efficacy of linzagolix administered orally once daily for up to an additional 6 months (for up to 12 months of treatment in total) in the subset of subjects who are treated with linzagolix up to the time point of interest. As such, the focus will be on subjects who received active treatment in the main study. The assessment of subjects who switched from placebo in the main study to active treatment in the extension study will be conducted as a secondary objective.

Subjects will be analyzed according to actual treatment received. The following four treatment groups will be analyzed: linzagolix 75 mg and linzagolix 200 mg with ABT fixed dose groups, linzagolix 75 mg and linzagolix 200 mg with ABT after 6 months placebo treatment. Only subjects with assessments at both baseline and the given time points will be included in the summaries. Baseline values are the same as in the main study (18-OBE2109-003 - Edelweiss 3), i.e. data collected prior to the treatment administration in the main study.

More details of the proposed statistical analyses will be described in the SAP, which will be written following finalization of the protocol and prior to database lock.

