6.2.6. Missing, Unused, and Spurious Data

6.2.6.1. Efficacy Endpoints Missing Data

Summary statistics will be based primarily on non-missing values. The planned statistical analyses aim to estimate the efficacy of linzagolix versus placebo while under randomized treatment and therefore lack of data after treatment discontinuation will not be considered as missing for these analyses.

There may be missing data during the screening period (from the main study) and whilst under treatment, for example, missed days of completing the eDiary. The primary analyses will use observed data only in such cases provided that a minimum number of completed daily eDiary

CRS-BS-TP-000005 V 2.0

entries are available. This effectively assumes that the individual values such as daily eDiary assessments (observed or not) are independent of being missing.

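### The SAP states a placebo comparison that an all-active extension cannot make, and the Month 12 co-primary responder rate lacks both an observed-only version and a within-subject measure of maintained response

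*SAP*

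**What the plan says.** **Stated aim.** SAP 6.4.2.1 opens with "The primary efficacy analysis aims to estimate the effect of linzagolix versus placebo on DYS and NMPP". SAP 6.2.6.1 repeats it: "The planned statistical analyses aim to estimate the efficacy of linzagolix versus placebo while under randomized treatment".

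**Design.** Protocol 8: "All subjects will receive once daily either linzagolix 75 mg alone (with ABT placebo) or 200 mg combined with ABT for 6 months". Women who had placebo in the main study are randomized 1:1 to one of the two active regimens. SAP 6.2.1 lists four analysis groups, none on placebo in the extension. SAP 6.2.4 plans no formal tests, and SAP 6.4.2.1.1 plans numbers and percentages of subjects.

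**Primary objective and target subjects.** Protocol 6.1.1 sets maintenance of efficacy as the primary objective and defines the co-primaries as "clinically meaningful reduction over the last 28 days of randomized treatment up to the Month 12 visit", with stable or decreased analgesic use. Protocol 7.1.1 ties the window to the four weeks before the Month 12 visit. Protocol 13.5 places the objective "in the subset of subjects who are treated with linzagolix up to the time point of interest" and adds: "Only subjects with assessments at both baseline and the given time points will be included in the summaries".

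**Early stoppers, co-primary rate.** SAP 6.4.2.1: "For subjects who discontinue treatment prior to Month 12 the last available observations prior to discontinuation will be used", namely the 28 days up to and including the last dose.

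**Early stoppers, secondary diary endpoints.** SAP 6.4.3 summarizes the endpoints of 6.4.3.1 to 6.4.3.24 in two ways. One sets discontinued subjects to missing at later months; the other carries their last 28 treated days forward.

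**The concern.** A reader of SAP 6.4.2.1 is told that the headline analysis estimates a placebo contrast. The tables will contain nothing of the kind, and the stated aim differs from the maintenance objective in Protocol 6.1.1 and SAP 1.2.

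The Month 12 composite rate is the trial's main result, yet it has fewer planned versions than the secondary diary endpoints. It pools genuine Month 12 data with data from women who stopped up to several months before, and no companion rate shows the women actually observed on treatment at Month 12.

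Responder rates at Month 6 and Month 12 show whether the group level is held. They do not show whether the same women kept their response, which is the more direct meaning of maintenance. Baseline 2 does not help, because SAP 6.2.2 defines it only for former placebo subjects.

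Last, a 28-day window counted back from an early last dose can reach before the first extension dose. For a woman switched from placebo, those days were spent on placebo.

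**Working it through.** **1. Group sizes (reproducing the plan's figure).** Protocol 13.2: 450 × 0.80 = 360 completers; 360 × 0.80 = 288 entrants. Both figures reproduce. Assuming equal continuation across main-study arms, 288 / 3 = 96 per arm: 96 in each continuous-active group, 96 / 2 = 48 in each placebo-switch group, and none assigned placebo in the extension.

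**2. Which planned outputs cover Month 12.**

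| Output | Covers the composite rate at Month 12, observed-only? |
|---|---|
| SAP 6.4.2.1.1 main analysis | No; while on treatment |
| Repeats at 75% and 35% diary completion; Ukraine exclusion (6.4.2.2) | No; same rule for stoppers |
| Per Protocol repeat | Not reliably. SAP 4.2 may exclude a Month 12 visit outside ±14 days, but does not name early discontinuation |
| SAP 6.4.3 and 6.4.3.1, DYS and NMPP change, two ways | Pain only; no analgesic component |
| SAP 6.4.3.1 distribution curves with thresholds marked | Pain only |
| SAP 6.4.3.7 responder rates | Visits other than Month 12; inside the two-way range, but told to follow 6.4.2 |

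**3. How old a Month 12 value can be.** Extension day 1 is Day 169, so extension day 28 is Day 196. The last scheduled dose is the day before Month 12: 337 − 1 = Day 336. A woman stopping on extension day 28 has a window ending 336 − 196 = 140 days before that dose.

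**4. Effect on the rate (illustrative).** Planned rate minus treated-to-Month-12 rate = d × (p_stop − p_treated), where d is the proportion stopping early. The only nearby figure is in Protocol 5.5.3: 12/176 = 6.8% withdrew for TEAEs in the Phase 2b extension. It counts adverse-event withdrawals only and comes from a different dose mix. 96 × 0.068 ≈ 6.5 women. With assumed response of 40% in one set of women and 70% in the other, the difference is 0.068 × (±0.30) = ±2.0 points. A wider assumed range (d of 5–30%, p_treated 70%, p_stop 20–90%) runs from 0.30 × (0.20 − 0.70) = −15.0 to 0.30 × (0.90 − 0.70) = +6.0 points.

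**5. What equal group rates say about retention.** With m responders among 96 at both visits, the fewest who can have responded at both is m − (96 − m).
- 60%, m = 58: 58 − 38 = 20, so 20/58 (34%) to 58/58.
- 70%, m = 67: 67 − 29 = 38, so 38/67 (57%) to 67/67.

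These are mathematical limits, not forecasts.

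**6. Precision of a retention proportion (Wilson 95% CI).**
- 46/58 (79%): 67.2% to 87.7%, half-width 10.3 points.
- 54/67 (81%): 69.6% to 88.3%, half-width 9.4.
- 52/58 (90%): 79.2% to 95.2%, half-width 8.0.
- 60/67 (90%): 80.0% to 94.8%, half-width 7.4.

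**7. Placebo days in the window.** For a stop on extension day k < 28, the window holds 28 − k main-study days: 21 at k = 7, 14 at k = 14, 8 at k = 20. The clause in SAP 6.4.3 allowing fewer than 28 days does not say which first dose it means, nor that it applies to 6.4.2. If the window is cut at the first extension dose it has k days, so k < 12 cannot meet the 12-entry minimum of SAP 6.4.2.1.1. Expected number: 96 switchers × 0.068 × 28/168 ≈ 1 woman, if stops are spread evenly over the 168 days.

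**The case against.** The placebo phrase is editorial. SAP 1.2 states the right objective, the four groups are listed, no tests are planned, and nobody could program a placebo contrast from the SAP. That stands. A reader might infer that the primary analysis is invalid; it is not, because no output depends on the phrase.

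A reader might also infer that the while-on-treatment rule breaches the protocol. The documents do not support that. Protocol 6.1.1 defines the endpoint over the last 28 days of randomized treatment, which fits the rule. Protocol 13.5 follows its treated-up-to-the-time-point wording by turning to subjects on active drug in the main study as against those switched from placebo, so it can be read as separating those two sets and not completers from stoppers. What remains is the requirement in 13.5 for assessments at the given time point, which the while-on-treatment rate does not meet and an observed-only rate would.

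The protocol names no retention endpoint, responder rates at other visits are planned, and derived data will be listed, so retention could be worked out afterwards. True, but a measure this close to the primary objective is better specified beforehand. The lower limits in step 5 are extremes: at 60%, all 38 Month 6 non-responders would have to become responders.

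The effect on the rate is small beside its sampling error (95% half-width about 10 points for 58/96), and the placebo-day problem is marginal. Both stand. Finally, counting discontinuers as non-responders answers a different question that the protocol does not ask. It is optional.

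**Conclusion.** The concern holds as a wording error plus gaps in the planned summaries. It is worth fixing because the changes are cheap and bear on the primary objective.

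- The stated placebo aim cannot be estimated and should be reworded; no result changes.
- The co-primary composite rate at Month 12 has no observed-only version, unlike the secondary diary endpoints. This is not a clear protocol departure. The shift is about 2 points either way at 6.8% stopping and assumed 40–70% response; the true discontinuation rate is not in the documents and could be higher.
- Maintenance is the primary objective, but no Month 6 to Month 12 within-subject measure is planned, and equal group rates do not determine it. The bounds rest on an assumed 96 per group and assumed response rates.
- The reach into placebo days follows from 6.4.2.1 as written, but probably touches about one woman and only a secondary objective.

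**What to change.** 1. In SAP 6.4.2.1 and 6.2.6.1, replace the versus-placebo aim with within-group response on active treatment.
2. Keep the planned rate. Beside it, report the Month 12 co-primary responder rate under the observed-only rule of SAP 6.4.3.
3. Add the proportion of Month 6 responders still responding at Month 12, with 95% CI, in the two continuous-active groups. State how Month 6 responders without a Month 12 value are counted.
4. State in SAP 6.4.2.1 that, for placebo-switch subjects, the 28-day window is truncated at the first extension dose, and that stops before extension day 12 then fall below the 12-entry minimum and are excluded.
5. State whether SAP 6.4.3.7 follows the two-way rule, and record in SAP section 7 how Protocol 6.1.1, 7.1.1 and 13.5 are read together.

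Cost: text edits plus 2 summaries × 2 co-primaries × 2 threshold sets = 8 descriptive result blocks, all from data already derived. The observed-only rate may come out higher or lower than the planned one.

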6.4.2.1.1. Primary Efficacy Analysis

The primary efficacy analysis will be conducted using the Treatment Extension Analysis Set.

The number and percentage of subjects with:

- Reduction of X for DYS,
- Reduction of X for NMPP,
- Stable or decreased use of analgesics for EAP during bleeding days, during non-bleeding days, and overall,
- Reduction of X for DYS and stable or decreased use of analgesics for EAP,
- Reduction of X for NMPP and stable or decreased use of analgesics for EAP,

will be presented.

There may be missing data during the screening period and whilst under treatment, for example, missed days of completing the eDiary. The primary analyses will use observed data only in such cases, provided that a minimum number of completed daily eDiary entries are available. This effectively assumes that the individual values such as daily eDiary assessments (observed or not) are independent of being missing. Subjects who have less than the minimum number of days available will be excluded from the analysis. This is valid under the assumption that such data is MAR, conditional on the baseline value.

The required minimum number of completed daily eDiary entries will be set to 12 days of each 28-day period (two Baseline menstrual cycles and the 28-day period prior to Month 12), i.e., 43% of non-missing assessments for the primary analysis, consistent with the use of 3 days per week as the minimum number of completed diary entries as suggested in recent research ((Griffiths & al, 2018), (Cappelleri & Bushmakin, Biopharmaceutical Report, 2020), (Cappelleri & Bushmakin, Biopharmaceutical Report, 2021)). The analysis will be repeated using subjects with at least 75% (21 days) and 35% (10 days) of completed daily eDiaries for DYS, NMPP and analgesic use.

The primary efficacy analysis will be repeated on the Per Protocol Extension Analysis Set.

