6.4.3.5. Change from baseline to Month 12 in dyspareunia (VRS)

Responses to the daily dyspareunia questions will be scored as follows. Responses on days where the subject was not sexually active for reasons other than their endometriosis will not be included in the analysis.

Response	Score
No pain during sexual intercourse.	0

CRS-BS-TP-000005 V 2.0

Page 47 of 99

Kissei / Cytel Confidential: This is a controlled document and shall not be changed, saved, copied or reproduced by any unauthorized person.

I was able to tolerate the pain during sexual intercourse.	1
Intercourse was interrupted due to pain.	2
I avoided sexual intercourse because of anticipation of	3
pain.	-

Mean dyspareunia scores for each subject will be calculated by averaging over the corresponding days during the 28 calendar days immediately prior to and including the last treatment administration date as defined in Section 5.2.1 (or the 28 calendar days immediately prior to and including the last dose date for subjects who discontinue treatment prior to Month 12). The baseline mean dyspareunia score will be calculated by averaging scores over the two baseline menstrual cycles.

Dyspareunia scores will be summarized using the TEAS, PP EAS and for the subgroup of subjects who have a mean dyspareunia score > 1 at baseline.

The number and percentage of subjects with a reduction of 0.9 from baseline to Month 12 for Dyspareunia will be presented. The reduction will be defined in a similar way as for the primary endpoint, but for Dyspareunia score and for the Month 12.

6.4.3.6. No analgesic use / no opiate use for EAP during the preceding 4-week period at each scheduled assessment

The analysis of the proportion of subjects reporting no analgesic use for EAP, and the proportion of subjects reporting no opiate use for EAP during the preceding 4-week period at each scheduled assessment will be conducted using descriptive statistics.

In addition to analgesic use for EAP as collected in the eDiary, concomitant medications in the study will be reviewed and medications to be considered as analgesic use for endometriosis associated pain will be confirmed by the Sponsor and be provided in an excel file prior to Database Lock. They may include any medication with the ATC codes from WHO drug dictionary version March 2016 as listed in Table 3

Table 3 List of ATC codes for analgesics and opioids

ATC code	Description
A03D	Antispasmodics in combination with analgesics

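### Dysmenorrhea is scored zero when no bleeding day is recorded, but only 12 of 28 diary days are required, so a bleed falling wholly on unrecorded days counts as no dysmenorrhea

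*SAP*

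**What the plan says.** SAP 6.4.2.1 defines the days that enter the DYS mean: "DYS will use days with uterine bleeding, defined as those days on which the subject records any uterine bleeding or spotting in the subject eDiary". The trigger for the zero rule is worded this way: "her daily eDiary reports indicate that she did not experience uterine bleeding on any days during the 28 calendar day period". In that event the SAP assigns the best possible score: "then the mean score for DYS will be set equal to zero (which reflects the absence of any DYS during that reporting time period". For Month 12 the window is the 28 calendar days up to and including the last treatment administration.

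A DYS responder needs a reduction of at least 1.10 from baseline (Month 3 threshold; 1.25 with the Month 6 threshold) and also stable or decreased analgesic use. For DYS, the analgesic component is averaged over the same recorded bleeding days as the pain score.

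SAP 6.4.2.1.1 handles missing diary days as follows: "The primary analyses will use observed data only in such cases, provided that a minimum number of completed daily eDiary entries are available". It then names the assumption behind that choice: "This effectively assumes that the individual values such as daily eDiary assessments (observed or not) are independent of being missing". On the size of the minimum: "The required minimum number of completed daily eDiary entries will be set to 12 days of each 28-day period". Two repeats are planned at other levels: "The analysis will be repeated using subjects with at least 75% (21 days) and 35% (10 days) of completed daily eDiaries".

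SAP 6.2.6.3 lets the next day's Yesterday answer replace a missing Today answer. It states this for analgesic use and IMP intake only, not for bleeding.

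**The concern.** Zero is a sound score when the diary affirmatively shows no bleeding. It is not sound when the bleeding days are simply blank. The SAP ties the zero to the absence of recorded bleeding, sets the completeness requirement separately at 12 entries, and never connects the two.

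The 12-day minimum is supported by reference to 3 entries per week. That argument concerns estimating an average from a sample of days. It does not support concluding that a clustered event never happened. Moreover, only the total of 12 is required, not 3 in each week, so a single 16-day gap passes.

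At stake is the DYS co-primary responder percentage. A woman whose whole bleed is unrecorded receives the best possible DYS score, whatever her pain was on those days.

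**Working it through.** **The plan's own figures.** 12/28 = 42.9%, stated as 43%, and 3 days × 4 weeks = 12. The repeats are 21/28 = 75% and 10/28 = 35.7%, stated as 35%. These reproduce.

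**Effect on the score.** With DYS set to 0, the reduction is baseline − 0 = baseline. A baseline of 1.10 or more meets the Month 3 threshold, and 1.25 or more meets the Month 6 threshold. A woman with baseline 1.5 and unchanged pain on her unrecorded bleeding days has a true reduction of 0 but is scored with a reduction of 1.5.

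**Chance that a bleed is wholly unrecorded.** Let n be the completed entries, m = 28 − n the missing days, and L the bleed length in days. From SAP 6.4.2.1.1, n is 12, 21 or 10. L is an assumption, shown at 3 and 5 days, because the documents give no on-treatment bleeding duration.

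- Random gaps: C(28 − L, n) / C(28, n). This is the SAP's own independence assumption.
- One unbroken gap, with the bleed placed uniformly in the window: (m − L + 1) / (28 − L + 1). This is an upper scenario.

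| Entries n | Bleed L | Random gaps | One unbroken gap |
|---|---|---|---|
| 12 (m = 16) | 5 days | C(23,12)/C(28,12) = 4.4% | 12/24 = 50% |
| 12 (m = 16) | 3 days | C(25,12)/C(28,12) = 17.1% | 14/26 = 53.8% |
| 21 (m = 7) | 5 days | C(23,21)/C(28,21) = 0.02% | 3/24 = 12.5% |
| 21 (m = 7) | 3 days | C(25,21)/C(28,21) = 1.1% | 5/26 = 19.2% |
| 10 (m = 18) | 5 days | C(23,10)/C(28,10) = 8.7% | 14/24 = 58.3% |

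Each figure is conditional on a woman having exactly that many entries and one bleed of that length inside the window. None is an estimate of how many women are affected.

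**What the table shows.** The independence assumption does not remove the problem, because the random-gap column already makes it. The 21-day repeat reduces it sharply for scattered gaps but less so for a single gap. The 10-day repeat is looser than the primary analysis.

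**The analgesic component.** With no recorded bleeding day there are no days over which to average analgesic use for DYS, and SAP 6.4.2.1 gives no rule for that case. The text therefore does not settle whether such a woman is a responder, and this component cannot be counted on as a safeguard.

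**The case against.** **The condition may be strict.** The zero applies when the diary reports indicate no bleeding on any day of the window, which could be read as requiring affirmative reports. The ambiguity is real. But no completeness condition is written, and no other handling is given for an incomplete diary with no bleeding recorded.

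**Long gaps should be rare.** Protocol 10.3.1 provides a daily alarm, missed-entry alerts and continuing remote checks, and compliance is checked at each visit. That makes a 16-day gap an upper scenario. Block gaps are still foreseeable: SAP 6.2.6.3 discards English-language subject entries from non-US sites after a device error and describes a change of diary vendor, and SAP 6.4.2.2 expects incomplete data from Ukraine.

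**The primary rule should not change.** This stands. SAP 6.4 derives endpoints as in the main study, and a different Month 12 rule would weaken comparison with Month 6, which the maintenance objective needs. Demanding more diary days only from women with no recorded bleeding would also select on outcome. The main-study SAP is not available here, so a further rule there cannot be excluded.

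**Two stronger readings are not supported.**

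- A reader might infer that missing days always favour response. That holds for the pain component only when every bleeding day is missed. Losing some bleeding days can move a non-zero mean either way; losing low-pain spotting days raises it.
- A reader might infer that the no-analgesic and no-opiate endpoints in SAP 6.4.3.6 share the defect. For analgesic data SAP 6.2.6.3 gives the next-day fallback, and SAP 6.4.3.6 adds a review of concomitant medications. The bleeding argument does not carry over.

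**Conclusion.** The gap holds for the DYS co-primary. Nothing in the SAP separates a bleed-free window from one in which the bleeding was not recorded, and where the whole bleed is missed the error can only favour response on the pain component.

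At the 12-entry minimum the conditional chance of a missed bleed is 4.4% to 17% for 5-day and 3-day bleeds with random gaps, and 50% to 54% with one 16-day gap. At 21 entries it is 0.02% to 1.1%, or 12.5% to 19% with one 7-day gap.

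A reader might go on to infer that the responder rate is inflated by amounts of this order. The documents do not support that: they contain no diary-completion or on-treatment bleeding data, and DYS response also depends on an analgesic component left undefined in this case. The net effect is unknown and could be small. The study plans no hypothesis tests, so what is affected is the reported percentage, not type I error or power.

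**What to change.** Keep the main-study derivation for the primary table. In SAP 6.4.2.1.1 add:

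- (a) The number of women per treatment group whose Month 12 DYS was set to 0, by number of completed bleeding entries and by longest run of missing days.
- (b) A sensitivity table for the DYS co-primary in which a zero is accepted only if there is no run of 3 or more consecutive missing bleeding entries. Treat the other women once as missing and once as DYS non-responders.

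Under (b), any bleed of 3 or more consecutive days must leave at least one recorded day; a 1- or 2-day bleed could still be missed. The 3-day cut-off is a judgement, not a figure from the documents.

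The cost is a derivation flag, the count and one more table, with no new data. The downside is that the sensitivity estimates are conservative for women who truly had no bleeding but kept sparse diaries.
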